Bwrdd Iechyd Prifysgol Abertawe Bro Morgannwg University Health Board

TITLE OF THE PROTOCOL:

ALOPECIA IN SURVIVORS OF CRITICAL ILLNESS: A MIXED METHODS STUDY

Short title/Acronym:

ASCRIM study

Sponsor:

ABMU Health Board

Representative of the Sponsor: [name] R&D Manager R&D Department Morriston Hospital [name]

REC reference:

16/NS/0133

STUDY SUMMARY/SYNOPSIS

TITLE	Alopecia in survivors of critical illness: a mixed methods			
	study			
SHORT TITLE	ASCRIM study			
Protocol Version	Version 5.2 18 th October 2017			
Number and Date				
Methodology	Observational and survey			
Study Duration	12 months			
Study Centre	Morriston Hospital, ABMUHB Princess of Wales, ABMUHB University Hospital Wales, CVUHB Royal Glamorgan Hospital, Cwm Taf UHB Prince Charles Hospital, Cwm Taf UHB Withybush Hospital, Hywel Dda UHB Glangwili General Hospital, Hywel Dda UHB Bronglais Hospital, Hywel Dda UHB Royal Gwent Hospital, ABUHB Nevill Hall Hospital, ABUHB Wrexham Maelor Hospital, BCUHB Glan Clwyd Hospital, BCUHB,			
Objectives	 To investigate the incidence and nature of patient- reported alopecia in survivors of critical illness. To investigate the risk factors for alopecia in survivors 			
Number of	of critical liness			
Number of Subjects/Patients	400 patients			
Main Inclusion Criteria	 ITU survivors with a ITU length of stay of ≥5 days Patients aged 18 years or more with capacity to consent and complete survey 			
Statistical Methodology and Analysis	Quantitative data analysis: Results from the data collection forms in the ICU and survey responses will be presented descriptively using numbers and percentages (categorical data) or median and interquartile ranges (continuous data). Risk factors will be analysed using Fisher's Exact test and multivariable logistic regression on SPSS (Chicago, Version 22). Missing data will be handled in the final analysis using a multiple imputation system.			

Protocol Agreement Page

The clinical study as detailed within this research protocol **(Version XXX, dated XX XXX)**, or any subsequent amendments will be conducted in accordance with the Research Governance Framework for Health & Social Care (2005), the World Medical Association Declaration of Helsinki (1996) and the current applicable regulatory requirements and any subsequent amendments of the appropriate regulations.

Chief Investigator Name: [name]

Chief Investigator Site: Morriston Hospital				
Contact details:	[contact]			
	Email: [contact]			

1. INTRODUCTION

1.1 Background / 1.2 Preclinical Data

Alopecia in adult survivors of critical illness has received limited attention in critical care research. During the acute critical illness phase, alopecia is of minimal concern to the intensive care team, when patient survival is the primary objective of care given. In the recovery phase of illness however, alopecia can prove distressing for the patient. Telogen effluvium is a form of non-scarring alopecia associated with the unanticipated termination of the normal growth phase in the hair follicle.(1) Telogen effluvium has been reported to occur after severe psychological stress, multisystem illness and with drug administration.(2-4)

Another type of hair loss that has been reported to occur in the critically ill paediatric population is traction alopecia and is caused by repetitive rubbing of the head on the pillow in patients confined to bed. This type of alopecia results in hair loss to a specific part of the head, normally the occiput.(5) Occipital alopecia and / or pressure sores were reported in 35% of patients in a recent study investigating outcomes in UK military casualties.(6) Limited research exists to date examining the epidemiology of alopecia in survivors of critical illness.

1.3 Clinical Data

In response to the work investigating alopecia in military survivors of critical illness(6), we undertook a small pilot study to investigate the incidence and nature of patient-reported alopecia in civilian survivors of critical illness. A total of 75 patients who had been discharged home for at least 12 weeks from our general ICU, attending the Follow-Up Clinic in 2014, completed a pre-designed alopecia survey. Median age was 65 years, with 35% males and a median ICU length of stay of eight days. A total of 17% of patients reported suffering alopecia. The severity of hair loss ranged between less than 10% to over 50%, with the location of hair loss varying between the patients. Duration of alopecia lasted between three weeks to seven months. The type of hair loss varied between patients, with only one patient reporting the additional loss of non-scalp hair. Five patients reported that complete regrowth had not occurred by the time they attended the clinic. There were no significant differences in demographic variables between the patients with and without alopecia.

The percentage of patients reporting alopecia was lower (17% versus 35%) than that reported by Scott et al (2014).(6) This could be due to the higher injury severity and longer median length of stay reported in the military cohort. The military cohort was also younger and all patients male, so further research into age and sex as risk factors for alopecia may be warranted. On analysis, no significant differences were found between the patients with and without alopecia in terms of age, sex, primary admission diagnosis and APACHE II score.

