2. TRIAL OBJECTIVES AND DESIGN

2.1 Trial Objectives

Primary Objective:

To investigate the incidence and nature of alopecia in adult survivors of critical illness

Secondary Objective:

To investigate the risk factors for alopecia in adult survivors of critical illness

Primary Endpoint:

Patient reported alopecia, measured using a pre-designed survey

Secondary Endpoint:

Patient reported alopecia, measured using a pre-designed survey

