Questionnaire study: This part of the study will be designed following available guidelines in questionnaire research and the guidelines published in a series of papers in the British Medical Journal.(7,8) A short questionnaire has been designed for the purpose of investigating incidence and nature of alopecia. The survey will be posted to the patients at three months post-ITU discharge, but if no reply is received after one month, then the survey will be administered over the telephone. In order to assess the clinical sensibility of the questionnaire, it was piloted on a number of ITU survivors attending our follow up clinic and as a result, a number of alterations were

made to the survey design. Both closed and open-ended questions are used in the survey.

The survey responses will be entered onto a paper case report form. Any survey with missing demographic data will still be included in the study and the remaining responses included in the analysis. Response rates will be recorded and non-responder analysis will be completed to compare the characteristics of the non-responders and the responders. Patients will be identified only by their hospital numbers once completed surveys are received.

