7.5 Statistical Analysis

Results will be presented descriptively using numbers and percentages (categorical data) or median and interquartile ranges (continuous data). Risk factors will be analysed using Fisher's Exact test and multivariable logistic regression on SPSS (Chicago, Version 22). Missing data will be handled in the final analysis using a multiple imputation system.

8. Data Handling & Record Keeping

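### One survey at three to four months right-censors any recorded duration of alopecia, and the summary rules in section 7.5 make no allowance for that

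*Protocol*

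**What the plan says.** Protocol section 2.1 gives the primary objective as "To investigate the incidence and nature of alopecia in adult survivors of critical illness". Section 1.3 uses the same pairing of incidence and nature for the pilot, and there describes hair loss by severity, location, type, duration and regrowth. On the last two it states that "Duration of alopecia lasted between three weeks to seven months" and that "Five patients reported that complete regrowth had not occurred by the time they attended the clinic". The pilot group is described as "A total of 75 patients who had been discharged home for at least 12 weeks from our general ICU", and "A total of 17% of patients reported suffering alopecia".

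For the present study, section 2.2 says "The survey will be posted to the patients at three months post-ITU discharge, but if no reply is received after one month", the survey is given by telephone. Section 4.6 repeats this schedule, and no later contact is planned. Section 7.5 has one rule for every continuous item, "median and interquartile ranges (continuous data", and sends missing data to multiple imputation. Neither rule has an exception for episodes that have not ended.

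**The concern.** By the protocol's own usage, the nature of alopecia includes how long it lasts and whether hair regrows. The pilot saw durations well beyond the point at which this study asks its only question. A patient still losing hair at the survey can give only a duration so far. If that figure is entered as complete, or left out, or left blank and imputed from patients whose hair loss has ended, the published duration can come out too short. Survivors and follow-up clinics would then be told that the problem passes sooner than the data can show. Response mode adds to this: a telephone respondent has about a month more observation than a patient who replies promptly by post.

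**Working it through.** The plan gives no computed figure for duration, so the check starts from the pilot.

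**Pilot count.** 17% of 75 = 12.75. Thirteen cases fit (13/75 = 17.3%) and twelve do not (16.0%). Incomplete regrowth: 5/13 = 38%, exact 95% CI 14% to 68%.

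**Longest observable duration.** Take hair loss starting on the day of ITU admission and the pilot's median stay of eight days (8/30.44 = 0.26 months).
- Survey at three months: 3 + 0.26 = 3.26 months.
- Telephone at four months: 4 + 0.26 = 4.26 months.

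Both fall short of seven months. To see a seven-month episode whole, the ITU stay would have to be 7 − 4 = 3 months (telephone) or 7 − 3 = 4 months (post).

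**When a quantile runs short.** Let *D* be the true duration and *w* the window from onset to survey. With ongoing cases entered at elapsed time, the recorded value is min(*D*, *w*). For a common *w*, its quantiles are those of *D* capped at *w*. The upper quartile is short only if P(*D* > *w*) exceeds 25%, and the median only if it exceeds 50%. When windows differ between patients these thresholds are approximate. If only resolved cases are kept, the distribution is that of *D* given *D* ≤ *w*, and every quantile is short.

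**Illustration.** The documents give neither the shape of the durations nor the time of onset, so both are assumed. Durations run from 21/30.44 = 0.69 to 7 months. Onset runs from ITU admission to one month after discharge. The share ongoing is:
- uniform: (7 − *w*)/6.31
- triangular, falling from its peak at 0.69: the square of that
- log-uniform: ln(7/*w*)/ln(7/0.69)

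Quantiles come from a simulation of 400,000 draws per shape. Each cell shows true / elapsed-time entry / resolved only, in months.

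| Shape | Survey, onset | *w* | Ongoing | Median | Upper quartile |
|---|---|---|---|---|---|
| Triangular | 4 months, ITU admission | 4.26 | 19% | 2.54 / 2.54 / 2.14 | 3.85 / 3.85 / 3.05 |
| Log-uniform | 3 months, ITU discharge | 3 | 37% | 2.20 / 2.20 / 1.44 | 3.93 / 3.00 / 2.08 |
| Uniform | 4 months, ITU discharge | 4 | 47% | 3.84 / 3.84 / 2.34 | 5.42 / 4.00 / 3.17 |
| Uniform | 3 months, ITU discharge | 3 | 63% | 3.84 / 3.00 / 1.85 | 5.42 / 3.00 / 2.43 |
| Uniform | 3 months, one month after discharge | 2 | 79% | 3.84 / 2.00 / 1.35 | 5.42 / 2.00 / 1.67 |

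The first and last rows are the extremes over these shapes and onset times. The resolved-only figures are short in every row. The elapsed-time median is short only in the last two, and the elapsed-time upper quartile in all but the first.

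**The case against.** The case against is substantial. Duration and regrowth are not named as endpoints; the only endpoint is patient-reported alopecia. The survey and case report form are not in the text. If duration is asked in bands, section 7.5 calls for counts and percentages, and median and interquartile range never apply. How to tabulate ongoing cases is detail that a protocol may leave to an analysis plan, and the pilot did report incomplete regrowth as a count. The 38% is a regrowth figure: hair loss may have stopped while regrowth is incomplete. The shapes in the illustration are stretched between the extremes of about 13 patients.

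All of this narrows the point without removing it. The single contact is fixed in the protocol, and no analysis plan can recover follow-up that was never made. Section 7.5 does state how continuous and missing data are handled, without an exception. The pilot gave a plain range of durations beside five patients not yet fully regrown, without saying whether those durations were complete; seven months may itself be an elapsed time. That does not suggest that censoring will be applied by default.

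A reader might go further and infer that the reported median is bound to be too short, or that most episodes will still be running at the survey. The documents support neither. The median survives elapsed-time entry while fewer than about half are ongoing, and a majority ongoing appears only under some of the assumed shapes and onsets.

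**Conclusion.** The point holds in a limited form. Any duration recorded at the single survey is right-censored for ongoing cases, at a time that differs by response mode. If duration is a continuous survey item, the stated summary runs short in these circumstances:
- always, if only resolved episodes are summarised;
- in the upper quartile, if more than about a quarter are ongoing and entered at elapsed time;
- in the median, only if about half or more are ongoing.

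Imputing blank ongoing durations from completed ones would also pull the summary down, because those values are missing for being long. The share ongoing is 19% to 79% under the assumed shapes and onsets; the documents do not fix it more closely.

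It would be wrong to call regrowth biased. Regrowth status at three to four months is valid for that time, but does not show eventual regrowth. Nor is half of the primary objective lost: nature also covers severity, location and type. Incidence, the risk-factor analysis and the sample size are not affected by this point.

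**What to change.** In section 7.5, add a rule for duration:
- Treat hair loss still under way at the survey as censored at the survey date, and summarise duration by Kaplan-Meier from reported onset.
- Do not impute ongoing durations from completed ones.
- Report separately the proportion with ongoing loss and the proportion with incomplete regrowth at the survey.
- State that resolution beyond three to four months after ITU discharge cannot be estimated.

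This needs the onset time, an ongoing-at-survey answer and the survey date for each affected patient; check that the survey and case report form hold them. If duration turns out to be banded, tabulate ended and ongoing episodes separately.

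The cost is a few lines of text and, at most, one or two survey items. The downside is that the median or upper quartile may not be reached, and must then be reported as such. Kaplan-Meier also assumes that the length of the window is unrelated to how long the hair loss lasts.

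A second contact with patients who report ongoing loss would extend the window, but it is a separate trade-off and not needed here. It would have to precede the anonymisation in section 8.1 and fit within the six months after recruitment in section 4.9.

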1.4 Rationale and Risks/Benefits

There are no known risks involved with participation in this non-interventional study. It is an observational study initially, with participants being requested to complete a short survey at the end of the data collection period. The potential benefit of the study is that risk factors for alopecia in critical illness survivors may be identified and care given to future high risk patients may be adapted accordingly.

2. TRIAL OBJECTIVES AND DESIGN

2.1 Trial Objectives

Primary Objective:

To investigate the incidence and nature of alopecia in adult survivors of critical illness

Secondary Objective:

To investigate the risk factors for alopecia in adult survivors of critical illness

Primary Endpoint:

Patient reported alopecia, measured using a pre-designed survey

Secondary Endpoint:

Patient reported alopecia, measured using a pre-designed survey

2.2 Trial Design

Mixed methodology study: Prospective observational and qualitative methods

Setting and sample

The study will be multi-centred, led from Morriston Hospital. There is currently no standardised protocol used for the assessment and measurement of alopecia on our ITU. All patients who survive their admission to ITU, between June and October 2017 and have an ITU length of stay of 5 or more days will be included in this study.

Definition of variables

The risk factors under investigation are the following: APACHE II score, age, primary admission diagnosis, fever, mechanical ventilation days, length of stay, sepsis, all relevant medications (known to cause alopecia), or transfusions during the ITU stay. This information will be collected prospectively during the patient's ITU stay. The Acute Physiology and Chronic Health Evaluation (APACHE II) score is used to predict mortality in ICU patients. The diagnosis of severe sepsis will be given using the definition provided by the 'Surviving Sepsis Campaign' (2008). Patients' primary admission diagnoses will be classified as either surgical (including abdominal, maxilla-facial, spinal, vascular conditions), general medical (including renal, oncology, respiratory conditions), neurological (acute and chronic) and trauma. 'Mechanical ventilation days' will be defined as the number of days the patient required invasive mechanical ventilation. ITU length of stay will be defined as the number of whole days the patient was managed on ITU or the high dependency unit (HDU).

Study design

In order to address both aims of this study a mixed methods approach will be used. An observational design for the prospective data collection and analysis of potential risk factors will be used, with a survey design for the survey completion. The patients recruited in the prospective study will be used for the questionnaire stage of the study, in order that the risk factors for alopecia can be investigated.

Prospective study: Data will be collected for all patients who survive an ITU length of stay of five or more days. Data will be recorded on a pre-designed spreadsheet and each patient will be allocated a study number.

Questionnaire study: This part of the study will be designed following available guidelines in questionnaire research and the guidelines published in a series of papers in the British Medical Journal.(7,8) A short questionnaire has been designed for the purpose of investigating incidence and nature of alopecia. The survey will be posted to the patients at three months post-ITU discharge, but if no reply is received after one month, then the survey will be administered over the telephone. In order to assess the clinical sensibility of the questionnaire, it was piloted on a number of ITU survivors attending our follow up clinic and as a result, a number of alterations were

made to the survey design. Both closed and open-ended questions are used in the survey.

The survey responses will be entered onto a paper case report form. Any survey with missing demographic data will still be included in the study and the remaining responses included in the analysis. Response rates will be recorded and non-responder analysis will be completed to compare the characteristics of the non-responders and the responders. Patients will be identified only by their hospital numbers once completed surveys are received.

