7.4 Sample Size

We aim to include sufficient patients in order that we can present the unadjusted and adjusted odds ratios and 95% confidence intervals for the risk factors for alopecia in survivors of critical illness. Vittinghoff and McCulloch (2007) suggested that the number of patients needed to ensure sufficient power in a cohort study is equivalent to five to nine events per variable (EPV) being investigated.(9) We will therefore use an EPV of 7 for this study. In this study we aim to investigate ten variables or risk factors therefore a minimum of 70 events (incidence of alopecia) were required. The previous pilot study completed by our research team reported an incidence of alopecia of 17% in survivors of critical illness, so we calculate that we need at least 400 patients in total. It would take two months to provide a sample of 400 patients (with a length of stay of 5 days to more) in the ITUs of all Welsh Hospitals, so we aim to recruit patients for four months to allow for mortality and loss to follow up.

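### If the standard APACHE II total is entered alongside age, the adjusted age odds ratio is not the effect of age at equal non-age severity; its bias depends on how severity acts (minor point)

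*Protocol*

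**What the plan says.** Section 2.2 (Definition of variables) gives the risk factors under investigation. The list opens with "APACHE II score, age, primary admission diagnosis, fever" and goes on to ventilation days, length of stay, sepsis, relevant medications and transfusions. APACHE II and age are separate entries. On the score itself, the section says only that "The Acute Physiology and Chronic Health Evaluation (APACHE II) score is used to predict mortality in ICU patients". It does not describe the components, and it does not say that a version without age points will be used.

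Section 7.4 states the aim to "present the unadjusted and adjusted odds ratios and 95% confidence intervals for the risk factors for alopecia". It sizes the study by events per variable: "We will therefore use an EPV of 7 for this study", and "we aim to investigate ten variables or risk factors therefore a minimum of 70 events (incidence of alopecia) were required". Section 7.5 names multivariable logistic regression, alongside Fisher's Exact test, as the method.

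Section 1.3 shows that age is a question in its own right. In explaining why a military cohort reported more alopecia than the pilot, it offers higher injury severity and longer stay as possible reasons. It then notes that "The military cohort was also younger and all patients male", and suggests further research into age and sex.

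**The concern.** On standard scoring, age contributes points to the APACHE II total. A model with that total and age therefore represents age twice. At a fixed total, moving to an older patient means moving to one with less acute or chronic non-age severity. The age coefficient then mixes the effect of age with the reverse of the severity effect. It does not answer what a reader would take it to answer: whether age matters among patients who are equally ill.

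This matters because section 1.3 raises two ideas together, that severity raises risk and that younger age may do so. If the first is true, the shared points lower the age odds ratio, which would look like support for the second. If older age truly raises risk, part of that effect would be hidden. Section 1.4 says that care of future high-risk patients may be adapted to the risk factors found, so the meaning of each adjusted odds ratio should be clear.

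**Working it through.** **The plan's own figure.** Section 7.4 uses 7 events per variable, ten variables and the pilot result, which "reported an incidence of alopecia of 17% in survivors of critical illness". That gives 7 × 10 = 70 events and 70 / 0.17 = 411.8, so 412 patients against a stated minimum of 400. At 400 patients, 400 × 0.17 = 68 events, or 6.8 per variable. The stated figure is reproduced to within rounding. The point here does not change it, because the fix leaves the number of coefficients the same.

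**Algebra.** Let P be the non-age points, A(age) the age points and T = P + A(age) the total. Suppose logit(risk) = c + g1·P + g2·age. Substituting P = T − A(age) gives logit(risk) = c + g1·T + g2·age − g1·A(age). If A rises roughly linearly at s points per decade and g2 is expressed per decade, the fitted age coefficient is about **g2 − g1·s**. The sign of the shift is the opposite of the sign of g1.

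**Assumptions not in the documents.** Age points of 0, 2, 3, 5 and 6 with cut-offs at 45, 55, 65 and 75 years; age mean 62 (SD 15); non-age points mean 14 (SD 6); a range for g1. With these, s is about 1.26 points per decade. The 17% event rate and the 400 patients are the protocol's.

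**Results with no true age effect (g2 = 0), model of total plus age.** The formula column is exp(−1.26 × g1). The large-sample column is a simulation of 300,000 patients. The last three columns are 1,500 simulated studies of 400 patients, tested at two-sided 5%.

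| OR per non-age point (g1) | Age OR per decade, formula | Large sample | Significant, younger worse | Significant, older worse | Two-sided |
|---|---|---|---|---|---|
| 0.951 (−0.05) | 1.065 | 1.059 | 0.4% | 8.4% | 8.8% |
| 1.000 (0) | 1.000 | 1.003 | 2.5% | 2.1% | 4.6% |
| 1.020 (0.02) | 0.975 | 0.973 | 4.9% | 0.8% | 5.7% |
| 1.051 (0.05) | 0.939 | 0.944 | 8.9% | 0.5% | 9.5% |
| 1.105 (0.10) | 0.882 | 0.882 | 23.6% | 0.1% | 23.7% |

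A separate run of 1,000 datasets per scenario agrees: age odds ratios of 0.96, 0.94, 0.91 and 0.89 at 1.03, 1.05, 1.08 and 1.10 per point, with two-sided rejection of 5.6%, 9.9%, 17.6% and 23.0%. Allowing a correlation of 0.2 between age and non-age points barely changes the large-sample values (1.060, 1.000, 0.974, 0.946 and 0.891 in the order of the table).

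**A true age odds ratio of 1.20 per decade.** The fitted value is 1.28, 1.20, 1.16, 1.13 and 1.06 in the same order. At 1.05 per point, power for age falls from about 51% to about 25%.

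**After removing the age points.** With no true age effect, the age odds ratio is 0.99 to 1.01 for every g1 tried, and two-sided rejection is 3.4% to 5.1%.

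**Collinearity.** The variance inflation factor is about 1.10 and the standard error for age rises by about 5%. The model is not unstable; the issue is what the coefficient means.

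**The case against.** **The final model is not fixed in the protocol.** Section 2.2 lists nine factors, section 7.4 counts ten, and section 7.5 states no selection rule or coding. Covariate derivation often sits in an SAP, and none is shown. This stands in part, and it is why the point is conditional. But the protocol itself names the score and age as separate risk factors and plans adjusted odds ratios sized on the number of variables. Followed as written, it leads to the total and age in one model.

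**The age points are outside knowledge.** True. They are part of how the named score is conventionally computed, but the protocol does not say so, and the slope of 1.26 per decade is assumed. On the log scale the shift is proportional to that slope: half the slope would turn 0.94 into √0.94 = 0.97.

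**The direction is not established.** A reader might infer that the plan is bound to produce a false finding that younger patients lose more hair. The documents do not support that. They give no severity effect size, and section 1.3 offers severity only as a possible explanation. The pilot found no significant difference for APACHE II or age, although with 75 × 0.17 ≈ 13 events it could not exclude a moderate effect.

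**The large error rates need strong effects.** A reader might also take away false-positive rates of 18% to 23%. These need odds ratios of 1.08 to 1.10 per point, that is 1.08^6 = 1.59 to 1.10^6 = 1.77 per assumed SD, and nothing in the protocol points to effects of that size. The simulation has two covariates. If ventilation days, sepsis or length of stay carry part of the severity effect, g1 shrinks and the shift with it; this was not simulated. Section 3.1 also says that the 400 allows for loss and non-response. Fewer analysed patients would leave the bias in the odds ratio but reduce the excess of false positives.

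**Unadjusted odds ratios will also be shown.** This helps, but only partly. With a correlation of 0.2, 1.05 per point and no true age effect, the unadjusted age odds ratio is about 1.05 and the adjusted one about 0.95. A reader could take that gap for ordinary confounding by severity.

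**Conclusion.** The point holds in conditional form and is minor. If the standard APACHE II total is entered with age, the adjusted age odds ratio is the contrast at equal total score. As an estimate of the age effect at equal non-age severity, it is biased in the direction opposite to the severity effect, and unbiased if severity has no effect. At 1.02 to 1.05 per point the shift is about 2% to 6% per decade, with two-sided false-positive rates of about 6% to 10%; an age odds ratio near 0.89 needs about 1.10 per point. These sizes rest on assumed scoring and distributions, a two-covariate model and 400 analysed patients. Only the secondary, risk factor objective is touched.

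**What to change.** Add one sentence to section 2.2 or 7.5: the multivariable model enters APACHE II minus its age points, alongside age. Keep the full total for the descriptive table and the unadjusted analysis. If the total is kept in the adjusted model for some other reason, state that the age odds ratio is then conditional on the total score.

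The cost is one derived variable. The age points follow from age, which is already collected, so no new data, patients or coefficients are needed. If an SAP already specifies this, a cross-reference is enough.
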